8. Marcello Di Martino, Javier García Septiem, Rocío Maqueda González, Jose Luis Muñoz de Nova, Ángela de la Hoz Rodriguez, Alba Correa Bonito, Elena Martín, Pérez. Cirugía electiva durante la pandemia por SARS-CoV-2 (COVID-19): análisis de morbimortalidad y recomendaciones sobre priorización de los pacientes y medidas de seguridad. Cirugía Española. 2020.

Hypothesis:

At Bellvitge University Hospital (HUB), a specific circuit was created in order to keep the emergent and the scheduled surgical activity that cannot be delayed, following measures of security established during the pandemic. We consider that this measures have contributed to contain the rate of infection of these patients and the post-operative complications that have occurred during the maximum crisis period, generating a control of quality of care and security.

For this reason, the sample of operated patients will be compared with a sample of patients adjusted to the month of January, before the crisis of the pandemic.

As a working hypothesis, we consider that there are no differences, and therefore, we propose the study as a non inferiority in terms of the assistance results.

Objective:

Our objectives are:

1. Assess all patients who have underwent surgery in our hospital during the period of maximum crisis of the pandemic, from March 11, 2020 to May 15, 2020.
2. Determine the post-surgical complications that have occurred during this period.
3. Determine the rate of COVID-19 infections in these patients and the secondary complications generated by them.
4. Be able to compare with series adjusted for types of surgery, characteristics of the surgery, age and sex in the pre-pandemic period (January 2020).
5. Propose some potential improvements in the context of the health crisis

Methodology:

Design and sample size:

Observational study, that includes all patients who have undergone emergent or scheduled surgery from March 11th 2020 until May 15th 2020, with a total of 789 surgical interventions recorded during this period.

Data collection:

Our source of information will be basically the access to the virtual clinical history (SAP) of the patients and the closing of the episode according to the Minimum Data Set (MDS). Only data of

interest for this research will be obtained, and in any cases, data that can be directly linked to patients (name, address, telephone number, etc.) will be used, preserving the confidentiality of the data. The variables of interest to be extracted from the clinical history to configure our data base will be:

- Age.
- Sex.
- Functional State according to ECOG (available in the annex).
- Personal antecedents of interest.
- Diagnosis of the pathology to be operated.
- Day of surgery.
- Type of surgery:
 - Specialty: general surgery, thoracic surgery, traumatology, neurosurgery, vascular surgery, neck and face surgery, urology...
 - If it consists on an emergent surgery or a scheduled surgery.
 - Delayable (benign) or non-delayable (malignant) surgery.
- Postoperative complications according to Clavien Dindo classification (available in the annex).
- Infection by COVID-19?
- Date of confirmation of the SARS-CoV-2.
- Treatment required by SARS; determined by groups.
- Hospital stay in days.
- Mortality.
- To assess the severity of the COVID-19 infection, we will use the Brescia Respiratory COVID19 Severity Scale (available in the annex).
- In addition, we will evaluate the therapeutic measures applied in each patient in case of COVID-19 infection (available in the annex).

Exclusion criteria:

1. Surgeries related to complications in the treatment of COVID patients.
2. Patients with incomplete data.

Selection criteria of the control sample (January 2020):

The selection will be made according to the type of surgery, sex and age range. In order to ensure that the sample is not inferior, the procedures chosen will be analysed with a ratio of 2:1 and 1:1 for patients undergoing emergent surgery, using as a reference the patients included during the COVID19 period, according to the list elaborated by Surgical Planification Department, where no operating results have been recorded (blind).

Statistical treatment:

It is considered a non-inferiority study, with a maximum difference in the percentage of patients with complications according to the Clavien Dindo classification of 10% and 2% in the percentage of patients with death result.

A descriptive analysis will be carried out using the usual statistical tests: Chi-square test to compare the category variables, and the subtraction of variables using parametric or non-parametric tests for the continuous variables (depending on the normality of the variables). For all the variables, bilateral tests with a significance level of 5% will be used.

It should be noted that the results will be analysed after the selection of patients included.

Possible limitations of the study:

The retrospective aspect of the study will limit the value of the study. There may be a lack of information about some interesting facts in the clinical history in the postoperative follow-up after the surgical episode at the HUB. In case that some important information is required and not reflected in the Shared Clinical History of Catalonia, it could be completed by telephone contact with patient and/or relatives to avoid information bias. In case of not having it, it will be treated as "missing data" in the subsequent analysis of the data.

Expected Benefits of the Project:

The comparison with the previous cohort will help us to know if there has been a higher rate of morbidity and mortality.

We will also analyse the rate of infection by COVID-19 in post-operative patients during this period of time.

This will allow us to know the complications and infections that occurred during this period of pandemic and we will be able to search and discover avoidable situations and establish our own circuits and protocols to avoid them in the future.

It will help us to establish a quality control in our centre, because, since now, it will be necessary to coexist with COVID-19 for an undetermined period of time (infections still happen daily and, by the moment, there is not a treatment or an effective vaccine to eradicate it)

If we are able to identify the weak points of our system, if they are detected, we will avoid repercussions on the health of our patients and we will adapt our health resources better.

Ethical Aspects:

As we have already mentioned, only data of interest will be obtained for the research and, in any cases, we will use data that can be directly related to the patients (names, surname, address, telephone numbers...) in order to keep the confidentiality of the data.

Both the centre and the researchers are responsible for data processing and are committed to complying with Regulation (EU) 2016/679 of the European Parliament and the Council of 27th April 2016 on Data Protection (RGPD), as well as other applicable laws and regulations (Organic Law 3/2018 on the Protection of Personal Data and the Guarantee of Digital Rights).

Data collected for the study will be identified by a code, so that it does not include information that could identify it, and only the principal investigators/collaborators will be able to relate these data to the patient and his/her clinical history.

Working Plan:

The timeline is as follows:

1. Presentation and approval by the Ethical Committee.
2. Selection of the study sample according to inclusion and exclusion criteria.
3. Selection of the historical cohort (January 2020) according to adjusted criteria based on surgical planning.
4. Creation of the database of study groups and historical cohort.
5. Analysis and introduction into the database of the patients in the groups based on the closure of the surgical episode.
6. Statistical analysis of the data.
7. Editing and publication.

A working team performed by faculty and residents of the Anaesthesiology and Reanimation Service Department, will collect all the previously mentioned data. It is estimated that in a period of 2 months it is possible to have all the necessary information collected for the analysis and presentation of the results.

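### January controls are chosen on surgery type, sex and age and compared without adjustment, so the non-inferiority comparison is open to residual confounding by patient fitness

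*Combined protocol and SAP*

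**What the plan says.** The Hypothesis section describes how pandemic patients reached theatre: "a specific circuit was created in order to keep the emergent and the scheduled surgical activity that cannot be delayed". The comparison group comes from January 2020, before the crisis.

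Under Methodology, Selection criteria of the control sample, the rule is: "The selection will be made according to the type of surgery, sex and age range". Controls are picked with the pandemic patients as the reference, from a surgical planning list that carries no operative results. The ratio is 2:1, with 1:1 for emergent surgery. Objective 4 speaks of "series adjusted for types of surgery, characteristics of the surgery, age and sex", which adds surgical characteristics but no measure of the patient's condition.

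The Data collection list includes ECOG functional state and "Personal antecedents of interest". Under type of surgery it places specialty, urgency ("If it consists on an emergent surgery or a scheduled surgery") and whether the operation could be delayed.

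Statistical treatment sets margins of 10 points for complications and 2 points for death. It names chi-square tests and parametric or non-parametric tests, two-sided at 5%. No regression, stratified, matched, standardised or propensity-score analysis appears. The limitations section mentions retrospective design and missing information, but not confounding.

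**The concern.** The activity kept running was "to keep the emergent and the scheduled surgical activity that cannot be delayed" safely, so who was operated on may have changed along with the conditions of surgery. Among patients of the same sex and age band having the same type of operation, triage could move fitness either way. Sicker patients who could not wait may be over-represented, or frail patients may have been deferred.

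The hypothesis is causal: the safety measures are said to have helped contain infection and complications. If pandemic patients were less fit, an unadjusted difference would overstate any worsening. If they were fitter, it would understate it and favour a false finding of non-inferiority. The two variables that best describe fitness are already in the data set, but the plan does not use them to address this.

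**Working it through.** The documents give no expected event rates and no ECOG distribution, so there is no planned figure to reproduce. The check has two parts: where each variable is used, and how far an imbalance could move the result.

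**1. Where each variable is used**

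| Variable | Collected | Control selection | Objective 4 | Adjusted analysis |
|---|---|---|---|---|
| Type of surgery | yes | yes | yes | none named |
| Emergent/scheduled | yes, under type of surgery | sets the ratio; matching not stated | possibly | none named |
| Delayable/non-delayable | yes, under type of surgery | not stated | possibly | none named |
| Age, sex | yes | yes | yes | none named |
| ECOG | yes | no | no | none named |
| Personal antecedents | yes | no | no | none named |

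**2. Shift in the risk difference from an ECOG imbalance**

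Shift = (risk at ECOG 2 or more − risk at ECOG 0-1) × (share with ECOG 2 or more in the pandemic group − share in January).

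Assumed, not from the documents: complications 20% at ECOG 0-1 and 40% at ECOG 2 or more (gap 20 points); deaths 1% and 6% (gap 5 points). The margins are the plan's own.

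| Imbalance | Complications | Share of 10-point margin | Death | Share of 2-point margin |
|---|---|---|---|---|
| 5 points | 0.05 × 20 = 1.0 | 10% | 0.05 × 5 = 0.25 | 12.5% |
| 15 points | 0.15 × 20 = 3.0 | 30% | 0.15 × 5 = 0.75 | 37.5% |
| 25 points | 0.25 × 20 = 5.0 | 50% | 0.25 × 5 = 1.25 | 62.5% |

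The sign reverses if the January group was the less fit.

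**3. Other assumed rates**

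The same quantity is risk in fit patients × (relative risk − 1) × imbalance. For a 10-point imbalance:

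- Complications, weak association: 0.20 × (1.5 − 1) × 0.10 = 1.0 point.
- Complications, 20% and relative risk 2: 0.20 × 1 × 0.10 = 2.0 points.
- Complications, 30% and relative risk 3: 0.30 × 2 × 0.10 = 6.0 points. This implies 30% × 3 = 90% complications in unfit patients, so it is an outer bound.
- Death, weak association: 0.01 × (1.5 − 1) × 0.10 = 0.05 points.
- Death, 1% and relative risk 3: 0.01 × 2 × 0.10 = 0.2 points.
- Death, 2% and relative risk 5: 0.02 × 4 × 0.10 = 0.8 points.

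A 20-point imbalance doubles each value.

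**4. Why an adjusted analysis must also contain urgency**

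Take 2:1 as two controls per scheduled case and 1:1 as one per emergent case. If half the pandemic cases are emergent (assumed), then for every 100 cases there are 50 emergent and 50 × 2 = 100 scheduled controls. The emergent share is 50% in the pandemic group and 50/150 = 33% among controls, a gap of about 17 points created by the sampling. If 2:1 means two cases per control, there are 50 emergent and 25 scheduled controls, and the share is 50/75 = 67%. Either way, a pooled comparison that ignores urgency does not compare like with like.

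**The case against.** Four counter-arguments have substance.

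- **Triage may already be partly covered.** The data list places urgency and delayability under type of surgery, emergent cases have their own ratio, and controls are chosen with the pandemic patients as reference. A reader might infer that controls are a sample of unrestricted January activity that ignores need. The documents do not support that. The selection sentence leaves open which sub-items are matched, but even full matching describes the operation and not the patient. Fitness within surgery type, sex and age band stays open.
- **ECOG is not wholly unused.** The statistical section applies two-sided tests to all variables, so a descriptive comparison of ECOG by period fits the plan. A reader might infer that ECOG is collected and never looked at; that goes too far. Showing an imbalance does not, however, remove it from the outcome difference.
- **No imbalance is shown.** This stands. A reader might infer that the comparison *is* confounded, but nothing in the documents establishes an imbalance or its direction.
- **The size is assumed.** This also stands. In the 5- to 25-point illustration the shift stays below both margins, so it changes the conclusion only when the true difference lies near one.

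Blind selection is no obstacle. The working plan selects controls before chart data are entered, so ECOG can come in at the analysis without touching that step.

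**Conclusion.** The gap holds as residual confounding by fitness, not as demonstrated bias. What the documents establish is that fitness measures are collected, that neither control selection nor any adjustment uses them, and that the named tests are unadjusted.

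Under the assumed rates, a 5- to 25-point imbalance moves the complication difference by 1.0 to 5.0 points and the death difference by 0.25 to 1.25 points. For example, with a 15-point imbalance a true worsening of 8 points in complications would appear as 8 + 3 = 11 points if pandemic patients were less fit, and as 8 − 3 = 5 points if they were fitter. These fall on opposite sides of the 10-point margin. With a true difference near zero the same shift would matter much less. Every input except the margins is an assumption. Adjustment should be specified before results are seen because size and direction cannot be known in advance.

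**What to change.** Keep the blind selection as it is, and add the following to Statistical treatment:

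- Estimate pandemic-minus-January risk differences in complications and in death, each with a confidence interval judged against its margin.
- Adjust them, by standardisation or a regression that yields risk differences, for ECOG (0-1 versus 2 or more), a simple coded comorbidity variable derived from personal antecedents, and emergent versus scheduled surgery. Report the unadjusted difference beside each.
- Define ECOG as the status before the surgical illness or admission, so that it is a true baseline.
- State how patients with missing ECOG stay in the analysis. At present the exclusion criteria drop patients with incomplete data, while the limitations section says unavailable information will be handled as missing. Without a rule, giving ECOG a role in the model could cost patients.
- Tabulate ECOG and comorbidity by period, and say which sub-items of type of surgery are matched.

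The cost is a paragraph of text, a baseline table, a coding scheme for personal antecedents (none is given now) and a retrospective reading rule for ECOG. No new patients or source data are needed. Deaths are likely to be few, so the mortality model must stay sparse. Some confounding, for instance by acute severity, would remain and belongs in the limitations.

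### Control ratios differ by urgency, but no analysis by urgency is named: a pooled comparison with January is unbalanced by up to 17 points in emergent share

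*Combined protocol and SAP*

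**What the plan says.** The section Selection criteria of the control sample (January 2020) chooses controls on three factors: "The selection will be made according to the type of surgery, sex and age range". It then sets the numbers: "the procedures chosen will be analysed with a ratio of 2:1 and 1:1 for patients undergoing emergent surgery". The same sentence anchors the choice of January patients on the pandemic cohort, "using as a reference the patients included during the COVID19 period". It does not say which surgery the 2:1 covers, or which side of the ratio is the control group.

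Statistical treatment frames the study as non-inferiority, with "a maximum difference in the percentage of patients with complications according to the Clavien Dindo classification of 10" per cent, and a corresponding 2% for death. No stratum is attached to either margin. For analysis it names a "Chi-square test to compare the category variables", parametric or non-parametric tests for continuous variables, and says that "bilateral tests with a significance level of 5% will be used". It names no stratified, weighted, matched or regression analysis, and no rule for comparing an estimate with a margin.

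Objective 4 is to "Be able to compare with series adjusted for types of surgery, characteristics of the surgery, age and sex in the pre-pandemic period". Urgency is collected: the variable list under Data collection includes "If it consists on an emergent surgery or a scheduled surgery".

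**The concern.** Matching at different ratios in two strata balances the cohorts within each stratum but not when the strata are pooled. If scheduled cases get two controls and emergent cases one, the control group is over-weighted with scheduled surgery. If emergent patients have more complications or deaths, the pooled January rate is then too low for the comparison, and the COVID period looks worse for a reason that has nothing to do with the pandemic. On the opposite reading (one control for every two scheduled cases) the distortion runs the other way and favours non-inferiority.

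The protocol intends to use the comparison to judge whether morbidity and mortality rose and to set hospital circuits. A case-mix artefact would mislead that use. Objective 4 asks for adjustment for characteristics of the surgery, and unequal ratios without weights do not deliver it for urgency.

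**Working it through.** **Inputs from the protocol:** ratios 2:1 and 1:1; margins of 10 and 2 points; two-sided 5% tests; 789 COVID-period interventions. The protocol states no emergent share, no risks by urgency and no power, so there is no figure of its own to reproduce.

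**Assumptions:** 2:1 applies to scheduled surgery; the nominal ratios are achieved; emergent shares and risks as shown below.

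**Step 1: emergent share among controls.** Let e be the COVID-period emergent share and k the number of scheduled controls per scheduled case, with one control per emergent case. The control share is e / (e + k(1 − e)). With k = 2 this is e/(2 − e); with k = 0.5 it is 2e/(1 + e).

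| e | controls, k = 2 | gap (points) | controls, k = 0.5 | gap (points) |
|---|---|---|---|---|
| 0.2 | 11.1% | 8.9 | 33.3% | 13.3 |
| 0.3 | 17.6% | 12.4 | 46.2% | 16.2 |
| 0.5 | 33.3% | 16.7 | 66.7% | 16.7 |
| 0.586 | 41.4% | 17.2 | 73.9% | 15.3 |
| 0.7 | 53.8% | 16.2 | 82.4% | 12.4 |

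The maximum gap is 17.2 points on either reading, at e = 0.586 (k = 2) or e = 0.414 (k = 0.5).

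**Step 2: bias.** With no true period effect, the bias of the crude difference is gap × (emergent risk − scheduled risk). For k = 2 and e from 0.2 to 0.7:

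- Complications, assumed risk gap 5 to 30 points: 8.89% × 5 = 0.44 points up to 17.16% × 30 = 5.1 points, or 4% to 51% of the 10-point margin.
- Death, assumed risk gap 1 to 6 points: 8.89% × 1 = 0.09 points up to 17.16% × 6 = 1.03 points, or 4% to 51% of the 2-point margin.
- To use one third of a margin, the risk gap must be at least 3.33/0.1716 = 19.4 points (complications) or 0.667/0.1716 = 3.9 points (death).

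**Step 3: one case by hand.** Take e = 0.5, k = 2, and assumed death risks of 1% scheduled and 5% emergent in both periods. The COVID-period rate is 0.5 × 5 + 0.5 × 1 = 3.00%. The control rate is (1/3) × 5 + (2/3) × 1 = 2.33%. The crude difference is 0.67 points although nothing changed. With 789 cases and 1,184 controls its standard error is √(0.03 × 0.97/789 + 0.0233 × 0.9767/1184) = 0.749 points. Power is Φ((2 − 0.67)/0.749 − 1.96) = Φ(−0.18) = 43%. The stratified estimate has no bias and a standard error of 0.834 points, so power is Φ(2/0.834 − 1.96) = Φ(0.44) = 67%.

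**Step 4: simulation.** 400,000 runs, e = 0.5, 789 cases, 1,184 controls (k = 2) or 592 (k = 0.5); chi-square without continuity correction; non-inferiority declared when the upper limit of a Wald 95% interval lies below the margin. That rule is an assumption, since the protocol states none. Each cell is crude / stratified by urgency.

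| Assumed risk, scheduled/emergent | Chi-square declares a difference, none true, k = 2 | Non-inferiority power, none true, k = 2 | False non-inferiority at the margin, k = 0.5 |
|---|---|---|---|
| Complications 20%/40% | 36% / 5% | 90% / 99.7% | 24% / 2.4% |
| Complications 25%/30% | 7% / 5% | 99.4% / 99.7% | 5.0% / 2.4% |
| Death 1%/5% | 15% / 5% | 43% / 67% | 8.8% / 2.5% |
| Death 2%/3% | 5.6% / 5% | 72% / 76% | 3.9% / 2.3% |

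With 600 cases and 900 controls (k = 2) the pattern is the same. Crude versus stratified power for death is 36% vs 56% (1%/5%) and 62% vs 65% (2%/3%).

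**The case against.** The strongest reply is that the protocol never commits to a pooled test. The ratio sentence is ambiguous and does not contain the word scheduled. The chi-square appears under a descriptive analysis and is not tied to the margins. Urgency sits under type of surgery, which is a selection factor, and Objective 4 promises adjustment. All this is true, and analysis by urgency is neither specified nor excluded. But selecting on urgency at unequal ratios is what creates the pooled imbalance, and a stated intention to adjust supplies no method that removes it. An analyst following the text would have only a chi-square on the pooled groups.

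The nominal ratios may also not be reached. At e = 0.5, k = 2 needs 1,184 controls from 31 January days (38 per day), against 789 interventions in 66 days (12 per day), and January's volume is not given. A shortage of scheduled matches would shrink the gap; a shortage of emergent matches would widen it. This stands, and it is why the fix should use realised ratios.

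The effect can also be small, as the 25%/30% and 2%/3% rows show. And false non-inferiority arises, when emergent risk is higher, only if k = 0.5. Taking the COVID-period patients as reference makes k = 2 the more natural reading, and there the bias works against non-inferiority. What remains on that reading is lost power, mainly for death, and a chi-square that can report case mix as pandemic harm.

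**Conclusion.** The concern holds. A pooled comparison under these ratios gives a difference biased by case mix whenever risk differs by urgency. The imbalance of up to 17.2 points follows from the nominal ratios alone. The resulting bias depends on an emergent share and on risks that the documents do not give, and could be anything from negligible to about half of either margin over the ranges shown. The 2-point death margin is the more exposed, because a mortality gap of about 4 points is enough to use a third of it. The conclusion assumes that 2:1 refers to scheduled surgery and that the cohorts are compared overall. This should be fixed before analysis. Confidence is medium, because the sentence is ambiguous and the size rests on assumed inputs.

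**What to change.** In the control-selection section, state which surgery each ratio covers (2:1 for scheduled, if that is what is meant) and which side of the ratio is the control group.

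In Statistical treatment, make the primary estimate for each margin a risk difference computed within emergent and within scheduled surgery and standardised to the COVID-period mix. With two controls per scheduled case this is the same as weighting scheduled controls 1/2 and emergent controls 1. Use the realised ratios if January does not supply enough matches. Compare the upper limit of a stratified, or matched-set robust, 95% confidence interval with the margin, and do not test pooled crude percentages.

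The cost is wording. Urgency is already collected, no patients are added and the ratios need not change. In the k = 2 examples the interval widens from 8.14 to 8.36 and from 8.01 to 8.25 points for complications (about 3%). For death it widens from 2.93 to 3.26 and from 2.77 to 2.91 points (11% and 5%).

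### 1:1 January controls for emergent surgery require a fall of at least 53% in daily emergent volume; the plan does not show this is feasible, and its unadjusted tests cannot absorb a shortfall

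*Combined protocol and SAP*

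**What the plan says.** Under Design and sample size, the cases are all patients with emergent or scheduled surgery "from March 11th 2020 until May 15th 2020, with a total of 789 surgical interventions recorded during this period". The Hypothesis section names the comparator as "a sample of patients adjusted to the month of January, before the crisis of the pandemic", and objective 4 and the Working Plan also fix it at January 2020.

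On control selection (Selection criteria of the control sample): "The selection will be made according to the type of surgery, sex and age range". The same section adds that "the procedures chosen will be analysed with a ratio of 2:1 and 1:1 for patients undergoing emergent surgery". Controls are chosen to resemble the pandemic cases, and they come from a planning list that carries no operative results.

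On activity, the Hypothesis section says that a dedicated circuit was set up "in order to keep the emergent and the scheduled surgical activity that cannot be delayed".

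Statistical treatment frames the comparison as non-inferiority, with margins of 10 percentage points for complications and 2 for death. The tests listed are chi-square for categorical variables and parametric or non-parametric tests for continuous ones. No regression, stratified or standardised analysis is mentioned.

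The available text does not give:
- January volumes, or the emergent/scheduled split of the 789;
- the direction of 2:1 (controls per case or cases per control);
- the width of the age bands, or whether a control may be reused;
- what happens to a case that has no control.

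**The concern.** The case window is more than twice as long as the control window. At a constant rate of emergent surgery, January holds fewer than half as many emergent patients as the case period. A 1:1 ratio is then out of reach unless emergent surgery fell sharply, and emergent work is what the hospital set out to keep.

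This matters because control selection is the only means of balancing case mix in the plan. If it falls short, nothing in the analysis makes up for it. Chi-square tests on the pooled groups would compare pandemic patients with controls of a different urgency and case mix. Complication and death rates plausibly differ between emergent and scheduled surgery, so such an imbalance could move either difference. The death margin of 2 points leaves little room for that.

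**Working it through.** The plan has no sample-size calculation to reproduce. The 789 is an observed count of interventions, and no control-group size is stated.

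**Inputs**
- Case window (Design and sample size): 21 days in March + 30 in April + 15 in May = 66 days inclusive.
- Control window (Hypothesis; objective 4): January 2020 = 31 days.
- Ratio (Selection criteria): read most naturally as 1:1 for emergent and 2:1 for scheduled surgery.
- Assumption: each January patient is used at most once.

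**Condition.** Let J be the January daily rate, P the pandemic daily rate and k the controls needed per case. Then 31 × J ≥ k × 66 × P, so J/P ≥ 66k/31. The fall in daily volume, 1 − P/J, must be at least 1 − 31/(66k).

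| Stratum and reading | k | J/P needed | Fall needed |
|---|---|---|---|
| Emergent, 1:1 | 1 | 66/31 = 2.13 | 1 − 31/66 = 53% |
| Scheduled, two controls per case | 2 | 132/31 = 4.26 | 1 − 31/132 = 77% |
| Scheduled, two cases per control | 0.5 | 33/31 = 1.06 | 1 − 31/33 = 6% |

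If one end date is excluded (65 days), the emergent figure is 1 − 31/65 = 52%.

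**Ceiling on emergent cases with a control**, for a fall f: min(1, 31/[66 × (1 − f)]).

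| Fall in daily emergent volume | Largest share with a 1:1 control |
|---|---|
| 0% | 47% |
| 20% | 59% |
| 30% | 67% |
| 40% | 78% |
| 50% | 94% |
| 53% or more | about 100% |

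Matching on type of surgery, sex and age range can only lower these shares.

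**In operations per day.** The emergent share of the 789 is not given. If it is assumed to lie between 20% and 80%, there are 158 to 631 emergent cases (2.4 to 9.6 per day over 66 days). January would then need 158/31 = 5.1 to 631/31 = 20.4 emergent operations per day.

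**Effect on the pooled comparison.** As an illustration, assume that half the cases are emergent, that scheduled controls are fully supplied and that emergent volume did not fall. Per 100 cases there are then 0.47 × 50 = 23.5 emergent controls.
- Two controls per scheduled case: the controls are 50/(50 + 100) = 33% emergent if the ratios are met, and 23.5/(23.5 + 100) = 19% with the shortfall, against 50% in the cases.
- Two cases per control: 50/(50 + 25) = 67% if met, and 23.5/(23.5 + 25) = 48% with the shortfall.

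The pooled urgency mix therefore depends on the undefined direction of 2:1 and on the size of the shortfall. Under the second reading, a shortfall happens to bring overall urgency back near the case mix, but the mix within emergent surgery can still differ. Under neither reading do the planned tests correct for the mix that results.

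**The case against.** The strongest reply is that the 53% is a condition, not a finding. January volume and the urgency split are not given, and the start of the background section, which may describe the change in activity, was not in the text available. Keeping emergent activity going says nothing exact about volume. All of this stands, and it rules out some stronger readings that a reader might infer:

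- *That the 1:1 ratio is unlikely to be met.* The documents do not show whether the fall reached 53%. They show only that feasibility has not been demonstrated.
- *That both ratios are in doubt.* Only the emergent ratio is demanding on either reading of 2:1. Scheduled surgery needs a fall of 77% or of 6%, and scheduled work was limited to what could not wait, so the lower figure could easily be met.
- *That unmatched cases will be dropped or loosely matched, and the hardest to match lost first.* The plan has no rule either way. Reuse of controls and a variable ratio are not excluded.
- *That a shortfall breaches the first objective, to assess all patients.* Objectives 1 to 3 describe the pandemic cohort, and only objective 4 is the comparison. The Working Plan selects the cases before the controls, and nothing removes a case for lack of a control.

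A further reply is that the unpaired tests and the wording on age range suggest frequency matching, so too few controls would cost only precision. That would be right if controls fell short in the same proportion in every stratum. The difficulty here is specific to emergent surgery, so the shortfall need not be proportional, and the unadjusted tests would carry the imbalance into the result. Reusing controls would avoid the shortage, but would break the independence that the chi-square test assumes.

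**Conclusion.** The concern holds as a feasibility and analysis gap. With each January patient used once, 1:1 emergent matching requires a fall of at least 53% in daily emergent volume; with no fall, at most 47% of emergent cases could have a control. The available text offers no count to show that this condition is met and no rule for the case where it is not.

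Because selection is the only case-mix control and the tests are unadjusted, a shortfall could bias the complication and death differences. The documents do not allow the size or direction of that bias to be computed. The conclusion rests on the inclusive dates, on reading 1:1 as the emergent ratio and on no reuse of controls. It does not depend on the direction of 2:1.

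**What to change.** 1. Before outcomes are seen, count January and case-period operations by urgency from the planning list, and state the counts in the plan.
2. State the direction of 2:1, the age bands and whether a January patient may serve more than once.
3. Keep every eligible pandemic case in the comparison, whether or not it has a matched control.
4. Estimate the complication and death differences, with confidence intervals set against the 10-point and 2-point margins, by regression or by standardisation to the pandemic case mix. Adjust for urgency, specialty, delayable or non-delayable status, age and sex, all of which are already on the data-collection list. Delayable status must be included because scheduled work in the pandemic was restricted on that basis.
5. Report how many cases had no control, by urgency.

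Optionally, use all eligible January operations, or lengthen the pre-pandemic window: 27 November 2019 to 31 January 2020 is 4 + 31 + 31 = 66 days. Either is a trade-off. A longer window changes the comparator period fixed in objective 4, and at unchanged volume it still would not supply two controls per scheduled case, which needs 132 days.

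The core change costs protocol wording and more analysis work, with no new variables. Enlarging the control pool adds some chart review. If deaths are few, the adjusted death difference will be imprecise, so the model for it should be kept small.
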